1.0 PROTOCOL SUMMARY AND/OR SCHEMA

In this pilot study, 20 patients with standard-risk medulloblastoma will be treated post-operatively with intrathecal 131-I-3F8, reduced-dose external beam radiation therapy (1800 cGy craniospinal + primary site boost to 5400 cGy via IMRT), and standard chemotherapy (vincristine, lomustine, cisplatin).

2.0 OBJECTIVES AND SCIENTIFIC AIMS

- To assess the feasibility of combining intrathecal radioimmunotherapy with external beam radiation therapy and chemotherapy.
- To maintain or exceed the current progression-free survival rate for patients with standard-risk medulloblastoma while using the protocol-prescribed regimen that is hypothesized to have less long-term serious morbidity.
- To evaluate the long-term morbidities in patients treated with this regimen, with specific attention to neuropsychological, neuroendocrine, audiometric and growth outcomes.

3.0 BACKGROUND AND RATIONALE

Brain tumors are a significant cause of mortality and severe morbidity in the pediatric age range. They are the most common type of solid tumor in children and recent data have suggested that their incidence has exceeded that of acute lymphoblastic leukemia to represent the most common type of cancer in children. About 3,000 cases are estimated to occur per year in the United States and 30,000 to 40,000 cases are estimated to occur per year worldwide.

Medulloblastoma and other central nervous system primitive neuroectodermal tumors have been estimated to represent 20 to 25% of pediatric brain tumors. SEER data have suggested that approximately 317 cases of medulloblastoma are diagnosed in patients aged 0 to 24 years in the United States per year, with approximately 218 in the group 3 to 24 years old. Approximately 1/2 of these patients are thought to have standard-risk disease, leading to an estimate of 110 patients per year potentially eligible for this study.

Patients with medulloblastoma are divided into 3 groups for clinical trials. Patients older than 3 years of age are divided into standard-risk and high-risk groups. Standard-risk (the group of subjects to be involved in this study) is defined as the absence of metastatic disease (disease beyond the primary site) and the lack of post-operative residual tumor at the primary site greater than 1.5 cm². High-risk disease is defined by the presence of either or both of those criteria. Patients less than 3 years of age are usually treated with protocols that attempt to avoid the use of RT due to the high risk of severe

Memorial Sloan-Kettering Cancer Center
IRB Protocol

IRB#: 02-088A(5)

neuropsychological damage associated with its use in these patients with immature brains.

Medulloblastomas are highly malignant tumors that are very unlikely to be cured by surgery alone due to either recurrence at the primary site or dissemination through the cerebrospinal fluid (CSF) to distant leptomeningeal sites. The use of post-operative RT can be curative. The historical approach was to use RT without chemotherapy, with doses of 3600 cGy craniospinal, with a boost to 5400 cGy to the posterior fossa. Several recent studies have indicated that this approach produces an approximate 5-year event-free survival rate of 60% in patients with standard-risk disease. However, these doses of RT are associated with a significant risk of severe chronic neuropsychological and neuroendocrine morbidities, and growth retardation, as will be described below. These problems can be ascribed both to the craniospinal component of the radiation treatment and also to the temporal lobe and auditory apparatus inadvertently receiving a significant proportion of the boost dose when conventional treatment techniques are utilized. An attempt to reduce the craniospinal dose to 2340 cGy without the addition of chemotherapy in patients with standard-risk disease resulted an increased risk of early relapse, early isolated neuraxis relapse and a strong trend towards lower 5-year event-free survival ($p=0.080$).¹

However, in single-arm studies, the addition of chemotherapy appears to both improve event-free survival and to allow the use of reduced-dose craniospinal RT. The Children's Cancer Group treated 65 children between 3 and 10 years of age with non-metastatic medulloblastoma with reduced-dose craniospinal RT (2340 cGy) and a boost to the posterior fossa to 5580 cGy. Patients also received weekly vincristine during the RT and beginning 6 weeks after completion of RT began a planned eight cycles of vincristine, cisplatin and lomustine chemotherapy. Progression-free survival was 86% +/- 4% at 3 years and 79% +/- 7% at 5 years. Hearing loss (presumably due to both cisplatin and RT to the auditory apparatus) occurred in 32%. Neuropsychological outcome was not described.² This regimen has been explored on a larger scale in CCG-9961. The study completed accrual in December 2000, but results are not yet available.

Only very limited data exist regarding the use of even lower craniospinal radiation doses. Investigators at the Children's Hospital of Philadelphia treated 10 children between 18 and 60 months of age with non-metastatic medulloblastoma with very reduced-dose craniospinal RT (1800 cGy) and a boost to the posterior fossa to 5040 to 5580 cGy. Patients also received weekly vincristine during the RT and beginning 6 weeks after completion of RT began a planned eight cycles of vincristine, cisplatin and lomustine chemotherapy. Actuarial survival at over 6 years was 70% +/- 20%. Of the 3 patients whose tumor recurred, in 1 recurrence was simultaneously appreciated in the primary site and distantly and 2 at distant sites only. IQ testing of the survivors suggested minimal neurocognitive damage.³

IRB
PB

Amended: 2/26/08

Memorial Sloan-Kettering Cancer Center
IRB Protocol

IRB#: 02-088A(5)

Neuropsychological outcome of children treated for medulloblastoma was assessed by investigators at St. Jude. They described 22 patients who were treated with RT only and whose craniospinal dose was randomly assigned to 3600 versus 2340 cGy. They noted that the patients that received the lower dose suffered less severe neuropsychological toxicity.⁴

Poor linear growth and adult short stature are extremely common in survivors of medulloblastoma and result from a combination of inadequate production of essential hormones such as growth hormone and thyroxine, and impaired spinal growth. In general, these abnormalities are directly correlated with the dose of radiation. Doses >3500 cGy to the hypothalamus result in growth hormone deficiency in 80-100% of subjects within 5 years.⁵⁻⁷ Similar doses administered to the whole spine are associated with a 60% incidence of primary hypothyroidism⁸ and an estimated loss in height in the range of 5 to 9 cm.⁹ Limited data suggest that reducing the dose of craniospinal RT from 2340 cGy to 1800 cGy would result in an improvement in growth and final height,¹⁰ as well as reduce the risks of neurocognitive dysfunction.¹¹

Preliminary Data

Radioimmunotherapy

The MSKCC neurosurgical staff reviewed the recent institutional experience of placing Ommaya reservoirs in patients for the treatment of prophylaxis of leptomeningeal metastases.¹⁷ Between January 1995 and June 1998, Ommaya reservoirs were placed in 107 patients. Complications occurred in 10 patients (9.3%) and included 2 infections, 5 catheter malpositions, and 3 intracranial hemorrhages. Two deaths occurred secondary to intracranial hemorrhage, but both had risk factors that should not apply to our patients. One was receiving anti-coagulation therapy for a mechanical heart valve and the other had thrombocytopenia secondary to other treatment.

Intensity modulated radiation therapy (IMRT)

IMRT is a new technology for the planning and delivery of RT. It represents a significant improvement over traditional 3-dimensional (3D) planning. IMRT features sophisticated

IRB
PB

Amended: 2/26/08

computer-optimized intensity distributions within a number of radiation beams. This is achieved by using an inverse-planning algorithm with dose and volume constraints for every target and critical tissue in the treatment field. Penalties are set for each constraint in order to set priorities among the various volumes. Treatment is delivered using dynamic multileaf collimators (tiny strips of metal shielding) whose movements throughout each field during the treatment are controlled by a computer. The result is a dramatically higher degree of conformality of dose to the target and significant sparing of adjacent healthy tissues.

IMRT is currently available in only a limited number of centers. There is only 1 publication that we are aware of reporting its use for patients with medulloblastoma. The authors noted that the auditory apparatus received lower doses of radiation when compared to historical patients treated with conventional techniques.¹⁸

We have treated 10 patients with newly-diagnosed medulloblastoma from July 1999 to the present with IMRT boosts and have shown a significant improvement in dose distributions for every patient compared to 2D and traditional 3D planning. In all cases, the dose conformality to the tumor target volume is improved while doses to the inner ears and other critical tissues are minimized. This decrease is expected to result in improved long-term hearing and a lower risk of endocrine dysfunction and neurocognitive delay, but this has not yet been proven. All 10 patients are currently event-free survivors, suggesting that the smaller boost volume does not adversely effect local control, but follow-up has been short (4 to 34 months, median 20 months, as of 5-31-02) and continued surveillance necessary.

4.0 STUDY DESIGN

This is a single-arm study of post-operative radioimmunotherapy (intrathecal 131-I-3F8), reduced-dose craniospinal radiation therapy (1800 cGy), primary site boost (to 5400 cGy) via IMRT and standard chemotherapy. Statistical stopping rules are defined to minimize the risk of excessive failures. Long-term neuropsychological, neuroendocrine, audiometric and growth parameters will be closely followed to assess long-term morbidities that are hypothesized to be reduced with this regimen.

5.0 THERAPEUTIC/DIAGNOSTIC AGENTS

5.1 131-I-3F8

Source and pharmacology: Monoclonal antibody 3F8 is a murine IgG3 antibody. It is raised in BALB/c mice and specifically recognizes the ganglioside GD2. Formulation and stability: 3F8 is stored as 2 mg/ml in pH 4.2 citrate phosphate buffer. Vials are stored at -80 C.

Route of administration: Intrathecal.

**Memorial Sloan-Kettering Cancer Center
IRB Protocol**

IRB#: 02-088A(5)

Supplier: 3F8 is produced using FDA guidelines for good laboratory practice within the premises of Memorial Sloan-Kettering Cancer Center. All lots have to pass sterility, safety, pyrogen, murine viruses, and DNA testing before human use. 131-I-3F8 is prepared by the Radiochemistry/Cyclotron Core Facility under the supervision of Dr. [name]. It is approved for human use via IND BB-IND-2299.

5.2 Vincristine

Route of administration: Intravenous

Supplier: Commercially available. NSC-67574.

Formulation: Clear liquid, 1 mg, 2 mg, and 5 mg vials.

Storage: Refrigerate. Protect from light.

Stability: Multiple-dose containers with preservatives are stable 30 days after opening if refrigerated.

5.3 Lomustine

Route of administration: Oral

Supplier: Commercially available. NSC-79037.

Formulation: 10 mg, 40 mg, and 100 mg capsules.

Storage: Room temperature.

5.4 Cisplatin

Route of administration: Intravenous

Supplier: Commercially available. NSC-119875.

Formulation: 50 mg vials.

Storage: Room temperature. Protect from light.

Reconstitution: Reconstitute each vial with sterile water to achieve a final concentration of 1 mg/ml. Cisplatin is compatible with KCl, mannitol, and magnesium but NOT NaHCO₃.

Stability: Reconstituted solution is stable for 20 hours at room temperature. May precipitate if refrigerated after reconstitution. Aluminum reacts with cisplatin causing

**IRB
PB**

Amended: 2/26/08

precipitate formation and loss of potency. Therefore, needles or intravenous sets containing aluminum parts that may come in contact with the drug must not be used for the preparation or administration of cisplatin.

6.0 CRITERIA FOR PATIENT/SUBJECT ELIGIBILITY

6.1 PATIENT/SUBJECT INCLUSION CRITERIA

- Patients must have histologic proof of medulloblastoma reviewed by the Department of Pathology at the Memorial Sloan-Kettering Cancer Center.
- Patients must begin study prescribed therapy within 42 days of neurosurgical resection of the tumor
- Age \geq 3-years-old.
- Post-operative head MRI must confirm $\leq 1.5 \text{ cm}^2$ of residual tumor is present.
- Head and spine MRI and lumbar CSF cytology must not show any definitive evidence of leptomeningeal dissemination (Chang stage M-0).
- Examinations evaluating extra-neural sites will not be mandated, but any performed for clinical indications must be free of metastatic disease.
- No prior RT or chemotherapy for the medulloblastoma is permitted.
- Patients must have adequate CSF flow (defined as lack of compartmentalization) on an 111-Indium DTPA flow study.
- Patients must have adequate organ function as defined by:
 - Hepatic: total bilirubin $< 2.0 \text{ mg/dl}$, AST $< 3 \times$ the upper limit of normal.
 - Renal: Calculated creatinine clearance or nuclear GFR $\geq 70 \text{ ml/min/1.73 m}^2$.
- The patient, or for minors, a parent or legal guardian, must give informed written consent indicating they are aware of the investigational nature of this study.

6.2 PATIENT/SUBJECT EXCLUSION CRITERIA

- Unable to start study prescribed therapy within 42 days of neurosurgical resection of the tumor
- Age less than 3 years
- $> 1.5 \text{ cm}^2$ residual tumor on post-operative head MRI
- Evidence of leptomeningeal dissemination on head or spine MRI or CSF cytology positivity
- Evidence of extra-neural metastases
- Prior radiation therapy or chemotherapy for the medulloblastoma
- Inadequate CSF flow on 111-Indium DTPA flow study
- Patients with signs or symptoms suggestive of increased intracranial pressure (headache, emesis, ocular paresis) will not be eligible until they are cleared by neurology and/or neurosurgery.
- Pregnancy
- Total bilirubin $\geq 2.0 \text{ mg/dl}$
- AST $\geq 3 \times$ the upper limit of normal
- Creatinine clearance and GFR $< 70 \text{ ml/min/1.73 m}^2$

7.0 RECRUITMENT PLAN

Patients will be offered the opportunity to participate in this trial if they meet the eligibility criteria. There will be no discrimination against females or minorities. Informed consent will be obtained from the patient, or if they are non-emancipated minors, their parent or legal guardian. Consent will be obtained by an investigator authorized to obtain consent. Patients will not receive any payment for their participation in this study.

8.0 PRETREATMENT EVALUATION

- Review of the pathology by the Memorial Sloan-Kettering Cancer Center Department of Pathology

- Post-operative head MRI
- Spine MRI
- CSF cytology obtained via lumbar puncture
- 111-Indium DTPA CSF flow study
- Liver function tests: Total bilirubin, AST
- Renal function tests: Creatinine clearance or nuclear GFR study
- For females \geq 12-years-old, pregnancy test
- All of these pre-treatment evaluations (other than pathology review) should have been performed \leq 30 days before registration onto study

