9.1.1 Premedications for 131-I-3F8

The following pre-medication guidelines are strongly suggested, but may be altered based on the clinical judgment of the investigators without being considered a protocol violation.

To start about 2 weeks prior to injection:

Levetiracetam (Keppra): Start at 10-20 mg/kg divided BID about 2 weeks prior to injection, after one week increase by 10 mg/kg. The pills come in 250 and 500 mg strength and no liquid preparation is currently available. For patients unable to tolerate oral tablets, phenytoin may be substituted. Taper of the anti-convulsant is recommended (decrease dose by about 50% 2 weeks post-injection, then discontinue medication 3 days later) rather than abrupt discontinuation.

To start about 5 days prior to injection:

IRB
PB

Amended: 2/26/08

SSKI: 7 drops daily (to begin 5 days pre-injection and to continue for 2 weeks post-injection)

Liothyronine (Cytomel): 25 mcg/day if weight less than 25 kg, 50 mcg/day if weight greater or equal to 25 kg (to begin 5 days pre-injection and to continue for 2 weeks post-injection)

To start 1-2 days prior to injection:

Dexamethasone (for those patients not already on a higher dose of dexamethasone): 0.5 mg po bid if weight less than 15 kg, 1 mg po bid if weight greater than or equal to 15 kg (to begin about 24 hours pre-injection and to be tapered over 1 to 2 weeks)

To be started about 1 to 2 hours before injection:

Hydroxyzine (Vistaril): 1 mg/kg IV, then Q 4 hours x 24 hours post-injection

Acetaminophen (Tylenol): 10 mg/kg po before injection and then Q4 hours x 24 hours post-injection

Lorazepam (Ativan): 0.05 mg/kg IV x 1

Hydromorphone (Dilaudid): 0.015 mg/kg/dose x 1, then PRN

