Neuroendocrine assessment performed at baseline will include standing and sitting height, Tanner staging of puberty, free thyroxine, TSH, and bone age x-ray. For patients > 12-years-old or who have \geq Tanner 2 puberty, LH/FSH, and testosterone or estradiol will be assessed. Follow-up examinations will be performed until 5 years post-diagnosis and will consist of standing and sitting height, Tanner staging, free thyroxine, and TSH every 6 months. Growth hormone stimulation testing will be performed if yearly growth velocity post-treatment is < 4cm per year or at 2 years post-completion of all therapy, whichever occurs first. Bone age x-ray, and LH/FSH, and testosterone or estradiol for patients > 12 years or who have \geq Tanner 2 puberty, will be performed annually.

Assessment of tumor status via brain MRI will be performed about 4 weeks after completing RT (pre-cycle 1 chemotherapy), then about every 3 months while on therapy (prior to cycles 3, 5, and 7). After completion of therapy, brain MRI scans will be performed about every 3 months for 1 year, then every 6 months for 2 years, then every 12 months for 1 year. Total spine MRI scans will be performed at about 1 year, 2 years, and 3 years post-completion of therapy. Subsequent scans will be performed at the clinician's discretion and are not mandated by this protocol, but brain MRI scans are recommended to be done about annually.

Mandated evaluations including lab work, audiograms, and MRI scans may be performed at other (non-MSKCC) centers if deemed clinically indicated by an investigator. Outside MRI scans should be submitted to PACS, and reports submitted to medical records, as soon as possible.

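### The required pregnancy test is timed from registration, not from the first 131-I-3F8 injection, and pubertal girls under 12 are not required to have one

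*Combined protocol and SAP*

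**What the plan says.** All references are to the combined protocol and SAP.

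- **Timing of the test.** Section 8.0 lists the pre-treatment evaluations and asks that all except pathology review be done no more than "30 days before registration onto study". The pregnancy test is on that list.
- **Who is tested.** Section 8.0 sets the threshold for females by age alone, at or above "12-years-old, pregnancy test".
- **The exclusion.** Section 6.2 excludes pregnancy with no age limit and no test date. The lower age limit for entry is 3 years (the exclusion reads "Age less than 3 years").
- **The only limit that reaches the start of treatment.** Section 6.1: "Patients must begin study prescribed therapy within 42 days of neurosurgical resection of the tumor". It runs from surgery, not from registration or from any test.
- **Lead-in.** Section 9.1.1 suggests an anticonvulsant: "Start at 10-20 mg/kg divided BID about 2 weeks prior to injection". The premedication guidelines as a whole "may be altered based on the clinical judgment of the investigators without being considered a protocol violation".
- **Exposure.** Section 9.1.2 gives 2 mCi intrathecally and then 10 mCi about a week later. External beam radiation and chemotherapy follow under sections 9.2 and 9.3.
- **Tests repeated later.** Section 10.0 repeats blood count, liver and renal function and audiograms before each cisplatin cycle. A pregnancy test is not among them.
- **Pubertal trigger elsewhere.** For sex-hormone testing, section 10.0 begins "For patients > 12-years-old or who have" and goes on to Tanner stage 2 or above.

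**The concern.** The plan makes pregnancy an exclusion, and the treatment combines radioiodine, craniospinal radiation and three cytotoxic drugs. The fact that matters is whether the patient is pregnant when treatment starts. The written rule establishes whether a test was negative at some point in the 30 days before registration. A pregnancy too early to detect at that test, or one that begins afterwards, meets every listed procedure and is then exposed.

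The second gap is one of coverage. The exclusion applies at every age, but the required check begins at 12. In its endocrine schedule the protocol allows for puberty at younger ages, and it does not carry that over to the pregnancy test.

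**Working it through.** The plan states no figure for the age of the test at dosing, so there is nothing to reproduce. The check is date arithmetic.

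**Inputs.** Screening window: 30 days before registration (section 8.0). Latest start of therapy: day 42, counting resection as day 0 (section 6.1). Interval between the two injections: about 7 days (section 9.1.2). Suggested lead-in: about 14 days (section 9.1.1). The gap *g* from registration to first injection is not given in the available text, so it is shown as a range.

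**Assumptions.** The first injection is taken as the start of study-prescribed therapy. Registration is no earlier than day 1, because histology and a post-operative MRI are needed first.

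**Formulas.**
- Maximum test age at the 2 mCi dose = 30 + *g*.
- Maximum test age at the 10 mCi dose = 30 + *g* + 7.
- If dosing is no later than day 42, the test must have been taken no later than day 42 − (30 + *g*) = 12 − *g* to reach that maximum.

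| Gap *g* (days) | Max age at 2 mCi | Max age at 10 mCi (about) | Latest test day that allows it |
|---|---|---|---|
| 0 | 30 days (4.3 weeks) | 37 days | day 12 |
| 5 | 35 days (5.0 weeks) | 42 days | day 7 |
| 7 | 37 days (5.3 weeks) | 44 days | day 5 |
| 12 | 42 days (6.0 weeks) | 49 days | day 0 |
| 14 | 44 days (6.3 weeks) | 51 days | day −2 |
| 21 | 51 days (7.3 weeks) | 58 days | day −9 |

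**The 14-day case in dates.** Test on day −2, registration on day 28, first injection on day 42: 42 − (−2) = 44 days. Second injection about day 49: 51 days.

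**What the 42-day rule does and does not cap.** A test on day *k* after resection is at most 42 − *k* days old at first injection: 41 days for *k* = 1 and 35 days for *k* = 7. A pre-operative test is not held to 42 days. Taken 7 days before surgery it can be 42 + 7 = 49 days old. The extreme is a test on day −29 with registration on day 1 and dosing on day 42, which gives 71 days.

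**Coverage, side by side.**
- Section 6.2: pregnancy excluded at any age.
- Section 8.0: test required at 12 or older.
- Section 10.0: hormone tests at over 12, or at any age with Tanner stage 2 or above.

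A girl under 12 at Tanner 2 or above therefore falls under the exclusion and the hormone trigger, but not under the required pregnancy test.

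**After the change.** If a negative result must fall within *W* days before the first injection, test age there cannot exceed *W*, whatever *g* is. With *W* = 30, purely to show the effect, the 44-day case becomes 30 days at most. The documents give no figure from which to choose *W*.

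**The case against.** The strongest reply is that the available text is incomplete. Section 10.0 says the mandated observations are tabulated in an appendix. The contents of Appendix B are not shown, and a part just before section 15.2 was removed. A registration-to-dose limit or a repeat test could be in either place. That stands as a caveat. It does not alter the anchor that section 8.0 states.

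Second, the longer intervals depend on a particular sequence. The 44-day case needs a test taken before surgery, registration at the end of its window, and premedication started at registration. Nothing ties premedication to registration, and it is not mandatory. This also stands: a reader might infer that a six-week-old test is typical or built in, and the documents support it only as a permitted schedule. The 30-day case needs none of that lead-in.

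Third, a reader might infer that girls under 12 are never tested. The documents do not say so. Testing is not required, but it is not barred, the exclusion still applies, and baseline Tanner staging should bring early puberty to notice. What is missing is any rule linking that finding to a pregnancy test. Nor do the documents equate Tanner 2 with menarche.

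Fourth, it is tempting to extend the criticism to every screening window, in particular to a CSF flow study that may predate the reservoir. That does not hold up. Section 9.1.2 confirms distribution by imaging about 24 hours after the 2 mCi dose, roughly a week before the 10 mCi dose, and section 9.1 calls for a flow study through the tubing when a shunt is used. Moving the window would not settle the order of flow study and reservoir placement in any case.

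**Conclusion.** The point holds for the pregnancy test. Section 8.0 verifies the exclusion relative to registration, while treatment exposure begins at the first injection. With same-day dosing the test may already be 30 days old at the 2 mCi dose. It may be 35 days old with a 5-day gap and 44 days old with a 14-day gap, with about 7 days more at the 10 mCi dose. The 42-day rule keeps a post-operative test under 42 days old but does not cap a pre-operative one. Pubertal girls under 12 are not required to be tested, although the exclusion covers them.

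The conclusion rests on three things: no limit or repeat test sits in the parts not shown, the 42-day limit is read as reaching the first injection, and the registration-to-dose gap is an assumption shown as a range. Few patients in a study of 20 would be affected, and the documents give no count. The sample size, the stopping rule and the progression-free survival assessment are untouched. It should still be changed, because the possible harm is serious and the remedy is small.

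**What to change.** In section 8.0, keep the pre-registration pregnancy test as part of eligibility, and add that a negative result is also required within a stated window before the first 131-I-3F8 injection. The sponsor should choose the window. Make Appendix B agree, or, if it already contains such a check, refer to it from section 8.0.

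Reconcile the age-only trigger in section 8.0 with the unrestricted exclusion in section 6.2 and the age-or-Tanner trigger in section 10.0, and state which patients must be tested. The threshold is a clinical decision for the sponsor.

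Leave the other eligibility evaluations tied to registration. Moving them all to the first injection would let tests that define eligibility fall after registration. It would also put anything done before day 12 out of a 30-day window for a patient dosed on day 42 (42 − 30 = 12), which could force repeat MRI, lumbar puncture and flow studies.

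The cost is a short wording change and an occasional repeat pregnancy test.
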